7.3.2. Subgroup Analyses for Objective Response Rate

Subgroups will be formed based on the following participant characteristics and baseline variables:

- Age: < 65 years, \geq 65 years
- Sex: male, female
- Race: White, others
- Geographic region: Europe, North America, rest of world
- Number of prior systemic therapy regimens: 1, 2-3
- Current Ann Arbor Staging: I-II, III-IV
- Bone marrow involvement at baseline: yes, no, unknown
- MIPI risk category: low (0-3), intermediate (4-5), high (6-11)
- ECOG performance status: 0, 1, 2

- Bulky disease at baseline: longest diameter ≥ 10 cm vs 5- < 10 cm, vs < 5 cm at baseline by IRC
- Relapsed/refractory status to the most recent prior therapy: relapsed, refractory, unknown

Subgroups may be further divided or combined based on emerging data. The ORR as determined by the IRC and its 95% exact binomial CIs will be provided for participants for each subgroup. A forest plot will be created to summarize the variability in ORRs as determined by the IRC for participants across subgroups.

7.4. Analysis of the Secondary Efficacy Parameters

7.4.1. Duration of Response

Duration of response is defined as the time from first documented evidence of CR or PR until disease progression or death due to any cause among participants who achieve an objective response (ie, CR or PR), as determined by revised response criteria for lymphomas ([Cheson et al 2014](#)). For responses assessed by the IRC, the date of initial response and date of disease progression will be provided by the Clinical Reviewer for participants who have achieved best response of CR or PR. Censoring of DOR will follow the same algorithm as the censoring of PFS (see Section 7.4.3).

The total number of responders as determined by the IRC, the number of participants whose disease progressed as determined by the IRC or who died, and the number of participants censored will be summarized. The Kaplan-Meier estimate of median DOR as determined by the IRC and its 95% CIs will be provided, with the CIs calculated using the generalization of Brookmeyer and Crowley's method (1982) with log-log transformation ([Klein and Moeschberger 1997](#)).

A sensitivity analysis of DOR will be performed where response assessments after the time of crossover will be excluded from the determination of DOR for participants who switched to the selected treatment regimen after starting the maintenance dose. Crossover participants who have not progressed at the time of crossover will be censored at the last valid radiologic assessment on/before the time of crossover. Participants who failed to achieve a response of CR or PR on/before the time of crossover will not be considered as responders for this analysis.

7.4.2. Complete Response Rate

Complete response rate is the percentage of participants with a best overall response of CR as defined by revised response criteria for lymphomas ([Cheson et al 2014](#)). For responses determined by the IRC, the best overall response for each participant will be provided by the Clinical Reviewer. Participants who do not have sufficient baseline or on-study response assessment information to be adequately assessed for response status will be included in the denominators in the calculation of CRR.

The CRR as determined by the IRC will be estimated with 95% CIs. Confidence intervals will be calculated based on the exact method for binomial distributions.

A sensitivity analysis of CRR will be provided to summarize participants who switched to the selected treatment regimen after starting the maintenance dose as a separate treatment regimen.

7.4.3. Progression-Free Survival

Progression-free survival is defined as the time from the date of the first dose of the study drug to the first documented disease progression as determined by revised response criteria for lymphomas (Cheson et al 2014), or death due to any cause, whichever occurs first. For response assessed by the IRC, date of disease progression will be provided by the Clinical Reviewer. Censoring for PFS will follow the algorithm outlined in Table 2, which is based on FDA Guidance for Industry: Clinical Trial Endpoints for the Approval of Non-Small Cell Lung Cancer Drugs and Biologics (2015) and Guidance for Industry: Clinical Trial Endpoints for the Approval of Cancer Drugs and Biologics (2018).

Table 2: Evaluation and Censoring of Progression-Free Survival

Situation	Outcome	Date of Progression or Censoring
No baseline tumor assessments	Censored	Day 1
No valid postbaseline response assessments	Censored	Day 1
Progression documented between scheduled response assessments	Progressed	Date of first overall response of PD
No progression	Censored	Date of last valid radiologic assessment (not NE and not missing)
Study discontinuation for undocumented progression	Censored	Date of last valid radiologic assessment (not NE and not missing)
Study discontinuation for toxicity or other reason	Censored	Date of last valid radiologic assessment (not NE and not missing)
New anticancer treatment started	Censored	Date of last valid radiologic assessment (not NE and not missing) on/before starting a new anticancer treatment
Death before first progressive response assessment	Progressed	Date of death
Death between adequate response assessments	Progressed	Date of death
Death or progression after 2 or more missed assessments	Censored	Date of last valid radiologic assessment (not NE and not missing) before the missed assessments

NE = not evaluable.

The total number of participants whose disease progressed as determined by the IRC or who died, and the number of participants censored will be summarized. The Kaplan-Meier estimate of median PFS as determined by the IRC and its 95% CIs will be provided, with the CIs calculated using the generalization of Brookmeyer and Crowley's method (1982) with log-log transformation (Klein and Moeschberger 1997). Progression-free survival rates at 6, 12, 18, 24, and 36 months will also be provided with 95% CIs calculated using Greenwood's formula to estimate the standard error.

A sensitivity analysis of PFS will be performed where response assessments after the time of crossover will be excluded from the determination of PFS for participants who switched to the selected treatment regimen after starting the maintenance dose. Crossover participants who have not progressed at the time of crossover will be censored at the last valid radiologic assessment on/before the time of crossover.

7.4.4. Overall Survival

[figure not shown]
Overall survival is defined as the time from the date of the first dose of study drug to death due to any cause. For participants who are still alive at the time of the analysis, OS will be censored on the date the participant is last known to be alive.

[figure not shown]
[figure not shown]
The number of participants who died and the number of participants censored will be summarized. The Kaplan-Meier estimate of median OS and its 95% CIs will be presented with the CIs calculated using the generalization of Brookmeyer and Crowley's method (1982) with log-log transformation (Klein and Moeschberger 1997). Survival rates at 6, 12, 18, 24, and 36 months will also be provided with 95% CIs calculated using Greenwood's formula to estimate the standard error.

7.4.5. Best Percent Change in Target Lesion Size

For each participant with measurable lesions at baseline, target lesion sizes will be measured by the sum of the product of diameters of all target lesions. The best percent change from baseline, defined as the largest decrease in target lesion sizes during the study, will be summarized, and a waterfall plot of the best percent change will be generated using data from the IRC. Note that for participants who only have increases in target lesion sizes from baseline, the smallest increase will be considered as the best change from baseline. For the IRC, there will be 2 radiologic reviewers for each participant. An adjudication will be performed per the Independent Review Charter when Reviewers 1 and 2 disagree on the CT/MRI best overall response, or when best overall response is consistent and the date of initial response and/or the date of PD differ between Reviewers 1 and 2. The adjudicator will choose the read that he or she believes most accurately represents the adjudication parameter(s) in question. This is considered the "accepted read," and data from this reviewer will be used for the analysis. When there was no adjudication needed, data from Reviewer 1 will be used for the analysis. An indicator is provided to identify the read that is considered to be the accepted assessment in data from the IRC.

Best change in target lesion size as reported by the investigator will also be summarized as described above. Target lesions considered "too small to measure" will be assigned a default value of 5 mm × 5 mm for the purposes of this analysis. Likewise, target lesions identified as "not present" at postbaseline assessments will be assigned 0 mm × 0 mm for this analysis. In the event a target lesion is unaccounted for in a particular postbaseline timepoint (ie, assessment missing or NE), then the overall sum of the product of diameters for target lesions will not be evaluable for that postbaseline timepoint.

9. SAFETY AND TOLERABILITY

[Appendix A](#) provides a list of planned tables, figures, and listings. Sample data displays are included in a separate document.

9.1. General Considerations

Summary tables may be replaced with listings when appropriate. For instance, an AE frequency table may be replaced with a listing if it only contains a few unique preferred terms reported on relatively few participants.

9.2. Adverse Events

9.2.1. Adverse Event Definitions

A TEAE is any AE either reported for the first time or worsening of a pre-existing event after first dose of study drug and within 30 days of the last administration of study drug regardless of starting new anti-lymphoma therapy. Analysis of AEs (as discussed below) will be limited to TEAEs, but data listings will include all AEs regardless of their timing in relation to study drug administration. For purposes of analysis, all AEs will be considered TEAEs unless the AE can unequivocally be defined as not treatment emergent.

Adverse events will be tabulated by MedDRA PT and SOC. Severity of AEs will be graded using the NCI CTCAE. CTCAE v4.03 is used for this study. The CTCAE reporting guidelines and grading details are available on the Cancer Therapy Evaluation Program website.

The subset of AEs considered by the investigator to be related to study drug will be considered to be treatment-related AEs. If the investigator does not specify the relationship of the AE to study drug, the AE will be considered to be treatment-related. The incidence of AEs and treatment-related AEs will be tabulated. In addition, serious TEAEs will also be tabulated.

9.2.2. Adverse Events of Special Interest

The number of participants who experienced TEAEs of special interest listed below will be summarized by maximum severity.

- Colitis
- Diarrhea
- Exfoliative dermatitis

- Febrile neutropenia
- Rash
- Intestinal perforation
- Pneumonitis
- Pneumonia
- PJP infection
- CMV infection
- Herpes simplex
- Varicella zoster virus infection

The time to onset of a TEAE is defined as the interval between the date of first dose of study drug and the date of the first occurrence of a TEAE. Participants who have not experienced a TEAE at the time of analysis will be right-censored at the earlier of 30 days after the last dose date and date of last study visit through the end of safety follow-up. If participants have missing or partial last dose dates of study drug or onset date of a TEAE, the partial or missing dates will be handled using the rules explained in Section 4.1.4.

Summaries of time to onset of new or worsening Grade 3 or higher AEs will be provided using descriptive statistics and the life-table method for rash, colitis, diarrhea, febrile neutropenia, pneumonia, herpes simplex, and varicella zoster virus infection. In addition, summaries of time to onset of new or worsening AEs of any grade will be provided using descriptive statistics and the life-table method for colitis, diarrhea, exfoliative dermatitis, intestinal perforation, pneumonia, pneumonitis, PJP infection, CMV infection, herpes simplex, and varicella zoster virus infection. Kaplan-Meier plots of time to onset of new or worsening Grade 3 or higher AEs will be provided for rash, colitis, and diarrhea. In addition, Kaplan-Meier plots of time to onset of new or worsening AEs of any grade will be provided for colitis and diarrhea.

Descriptive statistics of time to onset of these TEAEs of special interest are based on all participants who have experienced a TEAE at the time of analysis. To summarize these TEAEs of special interest using the life-table method, the effective sample size is defined as the number of participants at the beginning of the interval minus half the participants censored in the interval. The conditional proportion is calculated as the number of first events divided by the effective sample size in the interval.

The longest duration of a TEAE of any grade is defined as the longest interval between the date of occurrence of a TEAE and the date of resolution. The longest duration of a Grade 3 or higher TEAE is defined as the longest interval between the date of occurrence of a Grade 3 or higher TEAE and the date of improvement to Grade 2 or lower. If participants have missing or partial onset/end date of a TEAE, the partial or missing dates will be handled using the rules explained in Section 4.1.4. Participants who have missing end date of a TEAE at the time of analysis will be right-censored using the following algorithm:

- If the TEAE is serious, then the participant will be censored at the earlier date of data cutoff, study discontinuation and death.

- If the TEAE is not serious,
 - If the participant is ongoing with study treatment, then the participant will be censored at the data cutoff date, OR
 - If the participant discontinued treatment, then the participant will be censored at date of safety follow-up visit, or 35 days after the end of treatment visit (or after the last dose if the end of treatment visit was not performed), whichever is later; the censored date will be truncated by the earlier date of data cutoff, study discontinuation, and death if beyond.

Longest duration of new or worsening Grade 3 or higher colitis, diarrhea, rash, and febrile neutropenia will be summarized. In addition, longest duration of new or worsening AEs of any grade will be summarized for colitis, diarrhea, and rash.

The total number of participants whose TEAE of any grade resolved or whose Grade 3 or higher TEAE improved to Grade 2 or lower, and the number of participants censored will be summarized. The Kaplan-Meier estimate of median time to resolution/improvement and its 95% CIs will be provided, with the CIs calculated using the generalization of Brookmeyer and Crowley's method (1982) with log-log transformation (Klein and Moeschberger 1997). Resolution/improvement rates at selected timepoints will also be provided with 95% CIs calculated using Greenwood's formula to estimate the standard error.

TEAEs of special interest to be summarized may be adjusted based on emerging data.

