- Treatment A: INCB050465 20 mg once daily (QD) for 8 weeks followed by 20 mg once weekly
- Treatment B: INCB050465 20 mg QD for 8 weeks followed by 2.5 mg QD

Subjects will be evaluated for response by an IRC and followed for safety, DOR, PFS and OS. Subjects will receive treatment until disease progression, death, unacceptable toxicity, or consent withdrawal, whichever occurs first.

For each of the 2 cohorts, an interim futility analysis is planned when the first 30 subjects have been treated and evaluated for response or permanently discontinued study treatment because of disease progression, withdrawal of consent, or death. Cohort 1 will be terminated for futility if ≤ 3 of the 30 subjects have responded (ie, CR or PR) based on assessments provided by the IRC. Cohort 2 will be terminated for futility if ≤ 10 of the 30 subjects have responded (ie, CR or PR) based on assessments provided by the IRC. A timely assessment of response will be performed to avoid the risk of overenrollment. Safety will be evaluated by an Independent Data Monitoring Committee (IDMC).

To better understand the safety and efficacy of INCB050465, a total of 70 additional subjects (30 subjects in Cohort 1 and 40 subjects in Cohort 2) will be enrolled into one of the 2 treatment regimens (A or B) being evaluated in this study. The treatment regimen will be selected after enrollment is completed for either Cohort 1 or Cohort 2 (ie, 60 subjects enrolled) and after evaluation of emerging safety and efficacy data from this and other monotherapy studies of INCB050465 in NHL. Once a treatment regimen is selected, the non-selected treatment regimen will be closed to further enrollment. Subjects receiving the non-selected treatment regimen may switch to the selected treatment regimen or remain on their current treatment regimen, provided they have not met study treatment withdrawal criteria, and there are no safety concerns for their current treatment regimen. There will be no re-baselining for subjects who switch treatment regimens, and all subjects will continue to follow the same assessment schedule.

Cohort 1 will be closed to further enrollment by Protocol Amendment 7. Subjects already enrolled in Cohort 1 will continue to receive study treatment per protocol.

Study Population: Subjects with pathologically confirmed MCL, with documentation of either overexpression of cyclin D1 or t(11;14), who have had at least 1 but no more than 3 prior systemic treatment regimens.

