5.2. Treatment Groups

This is a Phase 2, open-label, 2-cohort study. All analyses will be conducted independently for Cohort 1 and Cohort 2, and there will not be multiplicity adjustment between the cohorts. Within each cohort, there will not be any statistical comparison between the treatment groups.

For analysis purposes, the 20 mg once weekly dosing period and the 2.5 mg QD dosing period in Group A and Group B, respectively, are considered maintenance dosing periods. Within each of the 2 cohorts, data will be presented in summary tables by actual received treatment regimen and combined, with an exception for participants who cross over to the selected treatment regimen after the start of the maintenance dosing period.

For participants who cross over from the initially assigned treatment regimen to the selected treatment regimen, if the crossover happens on/prior to the start of the maintenance dosing period then the participant will be summarized, according to the actual received treatment, in the selected treatment regimen; otherwise, the participant will be summarized in:

- A separate treatment regimen (ie, Crossover) for the safety summaries during the maintenance dosing period (eg. summaries of TEAEs and exposure).
- The initially assigned treatment regimen for all other summaries.

Per Protocol Amendment (Version) 7, Cohort 1 was closed to further enrollment. If the number of participants who have enrolled in Cohort 1 is relatively few, summary tables will be replaced with listings.

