9.2.3. Adverse Event Summaries

Overall summaries of TEAEs by treatment regimen will be provided during the INCB050465 initial QD dosing period, maintenance dosing period, and overall period (ie, all TEAEs regardless of the timing of occurrence). These summaries will include the following:

- Number (%) of participants reporting any TEAEs
- Number (%) of participants reporting any Grade 3 or higher TEAEs
- Number (%) of participants reporting any serious TEAEs
- Number (%) of participants reporting any TEAEs related to INCB050465
- Number (%) of participants reporting any Grade 3 or higher TEAEs related to INCB050465
- Number (%) of participants reporting any serious TEAEs related to INCB050465
- Number (%) of participants who had TEAE with fatal outcome
- Number (%) of participants with INCB050465 dose reductions because of TEAEs
- Number (%) of participants who temporarily interrupted INCB050465 because of TEAEs
- Number (%) of participants who permanently discontinued INCB050465 because of TEAEs

The following summaries will be produced for TEAEs during the overall period by MedDRA term (if 10 or fewer participants appear in a table, a listing may be appropriate):

- Summary of TEAEs by SOC and PT
- Summary of TEAEs by PT in decreasing order of frequency
- Summary of TEAEs by SOC, PT, and maximum severity
- Summary of TEAEs by PT and maximum severity in decreasing order of frequency
- Summary of Grade 3 or higher TEAEs by SOC and PT
- Summary of Grade 3 or higher TEAEs by PT in decreasing order of frequency
- Summary of serious TEAEs by SOC and PT
- Summary of serious TEAEs by PT in descending order of frequency
- Summary of INCB050465 treatment-related TEAEs by SOC and PT
- Summary of INCB050465 treatment-related TEAEs by PT in decreasing order of frequency
- Summary of INCB050465 treatment-related TEAEs by SOC, PT, and maximum severity
- Summary of Grade 3 or higher INCB050465 treatment-related TEAEs by SOC and PT
- Summary of INCB050465 treatment-related serious TEAEs by SOC and PT
- Summary of TEAEs with a fatal outcome by SOC and PT
- Summary of TEAEs leading to INCB050465 dose reduction by SOC and PT
- Summary of TEAEs leading to INCB050465 dose interruption by SOC and PT
- Summary of TEAEs leading to discontinuation of INCB050465 by SOC and PT
- Summary of selected TEAEs of special interest by maximum severity
- Summary of time to onset of selected TEAEs of special interest

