9.3.4. Worsening Laboratory Events of Special Interest

Laboratory events of special interest are listed below.

- ALT increased
- AST increased
- Absolute neutrophil count decreased

The time to onset of a worsening laboratory event is defined as the interval between the date of first dose of study drug and the date of the first occurrence of CTC grade worse than baseline for the laboratory event. Participants who have not experienced a worsening laboratory event at the time of analysis will be right-censored at the last postbaseline study visit with nonmissing CTC grade of the laboratory event.

Time to onset of worsening Grade 3 or 4 laboratory events of special interest will be summarized using descriptive statistics and the life-table method as described in Section 9.2.2, and the Kaplan-Meier plot of time to onset of worsening Grade 3 or 4 absolute neutrophil count decreased will be provided. Laboratory events of special interest to be summarized may be adjusted based on emerging data.

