- Section 4.1.4 was updated to include details of rules for handling partial/missing onset or end date of TEAEs in the calculation of time to onset or duration of a TEAE. Rules for partial/missing date of last dose were updated to include details for when both month and day are missing.
- Section 5.2 was modified to provide details regarding how crossover participants will be summarized.
- Section 5.3 was updated to remove the efficacy evaluable analysis set and use the FAS for all analyses of efficacy data. This change is to comply with comments from FDA that any participants who received at least 1 dose should be included in the efficacy analyses for a single-arm trial. The all-screened population was added for the summary of analysis populations.
- Section 6.1.1 was modified to add geographic region to the summary of demographic and baseline characteristics because it is one of the subgroups used for analyses on ORR.
- Section 6.1.2 was modified to remove summaries of tumor markers but only keep listings. Relapsed/refractory status to the most recent prior therapy was added to the summary table of disease history because the response to last regimen before entering the study may be a prognostic factor for clinical outcomes.
- Section 6.2 was modified to add summaries of participants who are ongoing with treatment or still in the study.
- Section 6.4 was modified to change the calculations of duration of treatment and average dose during the maintenance dosing period because Group B with 2.5 mg QD was selected as the maintenance dose.
- Section 7.3.1 was modified to replace the efficacy evaluable analysis set with the full analysis set. This change is to align with Protocol Amendment 7 dated 30 JAN 2020 and include all treated participants in the efficacy analyses to comply with comments from FDA.
- Section 7.3.2 was modified to add "unknown" as a category for bone marrow involvement at baseline. Relapsed/refractory status to the most recent prior therapy was added to the subgroup analysis because the response to last regimen before entering the study may be a prognostic factor for clinical outcomes.

- Section 7.4.3 was modified to update references of censoring for PFS.

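### By-regimen time-to-onset safety summaries keep late A-to-B switchers under A with no censoring at the switch, and no crossover-censored version is planned

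*SAP*

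**What the plan says.** - **Switching.** The Protocol synopsis (Overall Study Design) states: "Subjects receiving the non-selected treatment regimen may switch to the selected treatment regimen or remain on their current treatment regimen". There is no new baseline after a switch.
- **Direction.** SAP 11.2, in the Amendment 1 entry on Section 6.4, records that exposure calculations were changed "because Group B with 2.5 mg QD was selected as the maintenance dose". Crossover as SAP 5.2 defines it, a move to the selected regimen, is therefore from A to B.
- **Allocation.** In SAP 5.2, "data will be presented in summary tables by actual received treatment regimen and combined", with an exception for participants who cross over after maintenance starts. For maintenance-period safety summaries they form a separate Crossover group. Otherwise they go under: "The initially assigned treatment regimen for all other summaries".
- **Period.** SAP 9.2.3 introduces the list that contains the time-to-onset and life-table summaries with: "The following summaries will be produced for TEAEs during the overall period by MedDRA term". The shorter maintenance-period list, which uses the Crossover group, has no time-to-onset item.
- **Censoring.** SAP 9.2.2 measures onset from first dose, and participants with no event "will be right-censored at the earlier of 30 days after the last dose date and date of last study visit". In SAP 9.3.4, a participant with no worsening laboratory event is "right-censored at the last postbaseline study visit with nonmissing CTC grade of the laboratory event".
- **Efficacy.** For the PFS sensitivity analysis, SAP 7.4.3 says: "Crossover participants who have not progressed at the time of crossover will be censored at the last valid radiologic assessment on/before the time of crossover". SAP 7.4.1 has the matching rule for duration of response.

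**The concern.** A row labelled A should describe the toxicity of regimen A. Here it also contains time and first events that belong to B, from participants who changed regimen during maintenance. The two regimens are identical for the first 8 weeks, so any difference in onset between them must arise in maintenance, which is also when these switches occur. Protocol 1.3 and 5.4.4 report that in the earlier monotherapy study most immune-related events, and all but one of the events leading to discontinuation, came after about 9 weeks. That study used continuous daily dosing, so it shows only that late events are plausible here.

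SAP 7.3.1 already recognises that switchers received a mixture of maintenance regimens and could confound the efficacy evaluation of the non-selected regimen. The SAP adds crossover sensitivity analyses for ORR, CRR, duration of response and PFS (Tables 2.4.1 to 2.4.8). It plans none for adverse event or laboratory onset. At stake is how a reader interprets the A column of Tables 3.2.27 and 3.2.28 and, by the general rule in SAP 5.2, of Tables 3.3.6 and 3.3.7.

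**Working it through.** **1. Tracing one participant (hypothetical).** Someone assigned to A starts weekly maintenance, switches to B at month 6 and has a first Grade 3 colitis at month 9.
- Maintenance-period adverse event tables: shown under Crossover (SAP 5.2, 9.2.3).
- Overall-period onset tables: shown under A, with onset at month 9 (SAP 5.2, 9.2.2, 9.2.3).
- With no event at all, the time on B up to the censoring date counts as event-free time under A.
- With a switch on or before the start of maintenance, SAP 5.2 places the participant under B, so the problem does not arise.

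**2. What is stated and what is inferred.** For the adverse event tables the allocation follows from SAP 5.2 and 9.2.3. For the laboratory tables it follows from the general rule in SAP 5.2, since 9.3.4 does not restate it. SAP 5.2 speaks of summary tables, so display of Figures 4.5.1 and 4.6.2 by regimen is not stated.

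**3. Size.** The plan gives no figure to reproduce: no count of switchers, no switch dates and no event rates by regimen. The following is illustrative, and every input is an assumption.
- Event hazard 0.02 per month in the first 8 weeks and on A maintenance (hA); hazard on B maintenance (hB) = 0.5, 1, 2 or 3 times hA.
- A share s (25%, 50% or 75%) of those still event-free switches at month ts (4 or 6), unrelated to risk.
- Horizon T = 12 months.

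With censoring at the switch, A's incidence is 1 − exp(−0.02 × 12) = 21.3%.

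Under the SAP rule, A's event-free proportion is

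S(T) = S(ts) × [(1 − s) × exp(−hA(T − ts)) + s × exp(−hB(T − ts))].

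The share of A's first events that occur on B is S(ts) × s × (1 − exp(−hB(T − ts))) / (1 − S(T)).

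Worked case, ts = 4, s = 0.75, hB = 0.06:
- S(4) = exp(−0.08) = 0.9231.
- S(12) = 0.9231 × [0.25 × exp(−0.16) + 0.75 × exp(−0.48)] = 0.9231 × [0.2130 + 0.4641] = 0.625, so incidence is 37.5%.
- Share on B = 0.9231 × 0.75 × (1 − 0.6188) / 0.375 = 70%.

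| Switch month | Share switching | hB / hA | A's 12-month incidence, SAP rule | Share of A's first events on B |
|---|---|---|---|---|
| 4 | 75% | 0.5 | 16.4% | 32% |
| 4 | 75% | 1 | 21.3% | 48% |
| 4 | 75% | 2 | 30.1% | 63% |
| 4 | 75% | 3 | 37.5% | 70% |
| 6 | 25% | 0.5 | 20.1% | 6% |
| 6 | 25% | 1 | 21.3% | 12% |
| 6 | 25% | 2 | 23.6% | 20% |
| 6 | 25% | 3 | 25.5% | 26% |

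The other combinations fall within these ranges (16.4% to 37.5%; 6% to 70%).

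**4. Direction.** Eight weeks is 56 / 30.4375 = 1.84 months, which leaves 10.16 months of maintenance.
- Ratio 3: B's own incidence is 1 − exp(−(0.02 × 1.84 + 0.06 × 10.16)) = 47.6%. The true gap is 47.6 − 21.3 = 26.3 points; in the worst row above it reads 47.6 − 37.5 = 10.1.
- Ratio 0.5: B's incidence is 1 − exp(−(0.02 × 1.84 + 0.01 × 10.16)) = 12.9%. The gap of 21.3 − 12.9 = 8.4 points reads 16.4 − 12.9 = 3.5.

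In both cases A moves toward B. It moves up in one and down in the other.

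**5. Scale against noise.** If the first 60 participants in Cohort 2 split equally (assumed), A has 30. Ignoring censoring, the standard error of 21.3% is √(0.213 × 0.787 / 30) = 7.5 points. The shifts above run from −4.9 to +16.2 points.

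**The case against.** The strongest reply is that little depends on these outputs. SAP 3.2 and 5.2 rule out any statistical comparison of the regimens. The combined column is correct. SAP 11.2 describes the initial- and maintenance-period tables as the support for the maintenance dose's safety profile, and the maintenance-period tables already separate late switchers. This stands, and it limits the severity.

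A reader might infer four stronger things that the documents do not support.
- *That the rule makes A look worse.* The documents report no toxicity of B relative to A, and Protocol 1.4 proposes both regimens as ways to reduce events leading to withdrawal. A can read too high, too low or correctly.
- *That the late A profile mostly describes participants on B.* The number of switchers is not given. Selection comes only after 60 participants are enrolled in a cohort and emerging data are reviewed, so many switches may come well after week 9.
- *That these summaries are meant to display a difference between A and B.* No section says so.
- *That censoring at the switch should replace the planned analysis.* In SAP 7.4.1 and 7.4.3 it is a sensitivity analysis only. As a replacement it would drop events soon after the switch that may be due to A, although the SAP counts events to 30 days after last dose. It would also make the A counts in Table 3.2.27 disagree with those in Table 3.2.26.

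**Conclusion.** The point holds for switches after the start of maintenance. SAP 5.2, 9.2.2, 9.2.3 and 9.3.4 together count first events and event-free time on B under A in the by-regimen onset summaries, and no planned output gives an A onset profile free of B exposure. The distortion pulls A toward B. Its sign depends on the unknown relative hazards, and it vanishes if they are equal.

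Its size cannot be determined from the documents. The illustrated range (16.4% to 37.5% against 21.3% at 12 months) rests wholly on assumed hazards, switch times and switching shares, and on switching being unrelated to risk. With about 30 participants under A, many of the illustrated shifts are no larger than sampling error. Severity is low to moderate: a descriptive safety output is mislabelled in part, and no efficacy conclusion or formal test is affected.

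**What to change.** Add to SAP 9.2.2 and 9.3.4, in line with 7.4.1 and 7.4.3:

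*For by-regimen time-to-onset outputs (Tables 3.2.27, 3.2.28, 3.3.6, 3.3.7, and Figures 4.5.1 and 4.6.2 if shown by regimen), a sensitivity analysis will censor participants who switch to the selected regimen after starting maintenance at the date of crossover; first events after crossover will be presented under Crossover. The combined column is not censored at crossover.*

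The planned versions stay as they are. The crossover date is already needed for the duration of response and PFS sensitivity analyses, so the added work is one censoring variable and a second set of outputs. No treatment, visit or data collection changes.

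The sensitivity version has three costs:
- Follow-up under A is shorter, with few or no participants at risk late. If everyone switches, late A estimates do not exist.
- Censoring may be informative, because switchers must not have met withdrawal criteria.
- Events soon after the switch that may be due to A are not counted under A, so the two versions should be read together.
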